12.2 Adverse Event Reporting

12.2.1 Definitions

The following definitions of terms apply to this section:

Adverse event: Any untoward medical occurrence associated with the use of a drug in humans, whether or not considered drug related.

Life-threatening adverse event or life-threatening suspected adverse reaction: An adverse event or suspected adverse reaction is considered "life-threatening" if, in the view of either the investigator or sponsor, its occurrence places the patient or subject at immediate risk of death. It does not include an adverse event or suspected adverse reaction that, had it occurred in a more severe form, might have caused death.

Serious adverse event or serious suspected adverse reaction: An adverse event or suspected adverse reaction is considered "serious" if, in the view of either the investigator or sponsor, it results in any of the following outcomes:

- Death
- Life-threatening adverse event
- Inpatient hospitalization or prolongation of existing hospitalization
- Persistent or significant incapacity or substantial disruption of the ability to conduct normal life functions
- Congenital anomaly/birth defect
- Important medical events that may not result in death, be life-threatening, or require hospitalization may be considered serious when, based upon appropriate medical judgment, they may jeopardize the patient or subject and may require medical or surgical intervention to prevent one of the outcomes listed in this definition. Examples of such medical events include allergic bronchospasm requiring intensive treatment in an emergency room or at home, blood dyscrasias or convulsions that do not result in inpatient hospitalization, or the development of drug dependency or drug abuse.

Events not to be considered as AEs/SAEs:

- Medical conditions present at the initial trial visit that do not worsen in severity or frequency during the treatment plan are defined as baseline medical conditions and NOT to be considered AEs/SAEs
- Visits to the emergency room or other hospital department < 24 hours, that do not result in admission (unless considered an important medical or life-threatening event)
- Elective surgery, planned prior to signing consent, and admissions for a planned medical/surgical procedure
- Admission encountered for another life circumstance that carries no bearing on health status and requires no medical/surgical intervention (eg, lack of housing, economic inadequacy, caregiver respite, family circumstances, administrative reason)
- Admission for administration of anticancer therapy in the absence of any other SAEs.

Suspected adverse reaction: Any adverse event for which there is a reasonable possibility that the drug caused the adverse event. For the purposes of IND safety reporting, "reasonable possibility" means there is evidence to suggest a causal relationship between the drug and the adverse event. Suspected adverse reaction implies a lesser degree of certainty about causality than adverse reaction, which means any adverse event caused by a drug.

Adverse reaction means any adverse event caused by a drug. Adverse reactions are a subset of all suspected adverse reactions where there is reason to conclude that the drug caused the event.

Unexpected adverse event or unexpected suspected adverse reaction: An adverse event or suspected adverse reaction is considered "unexpected" if it is not listed in the investigator brochure or is not listed at the specificity or severity that has been observed; or, if an investigator brochure is not required or available, is not consistent with the risk information described in the general investigational plan or elsewhere in the current application, as amended. For example, under this definition, hepatic necrosis would be unexpected (by virtue of greater severity) if the investigator brochure referred only to elevated hepatic enzymes or hepatitis. Similarly, cerebral thromboembolism and cerebral vasculitis would be unexpected (by virtue of greater specificity) if the investigator brochure listed only cerebral vascular accidents. "Unexpected," as used in this definition, also refers to adverse events or suspected adverse reactions that are mentioned in the investigator brochure as occurring with a class of drugs or as anticipated from the pharmacological properties of the drug, but are not specifically mentioned as occurring with the particular drug under investigation.

12.2.2 Eliciting AE Information

Research subjects will be routinely questioned about AEs at study visits.

12.2.3 Recording Requirements

All observed or volunteered adverse events (serious or non-serious) and abnormal test findings, regardless of study group or suspected causal relationship to the study drug(s) will be recorded in the subjects' case histories. For all adverse events, sufficient information will be pursued and/or obtained so as to permit 1) an adequate determination of the outcome of the event (i.e., whether the event should be classified as a serious adverse event) and; 2) an assessment of the causal relationship between the adverse event and the study drug(s).

Adverse events will be followed until resolution while the patient remains on-study. Once the patient is removed from study, events thought to be related to the study medication will be followed until resolution or stabilization of the adverse event, or until the patient starts a new treatment regimen, or death, whichever comes first. Subjects will be followed for AEs/SAEs for 30 days after their last dose of study drug(s).

AEs or abnormal test findings felt to be associated with the investigational drug or

study treatment(s) will be followed until the event (or its sequelae) or the abnormal test finding resolves or stabilizes at a level acceptable to the Sponsor-Investigator.

12.3 CAUSALITY

The investigator must determine the relationship between the administration of radiation and study drug(s) and the occurrence of an AE/SAE as defined below:

- Definitely Related – The AE is clearly related to radiation and/or study drug(s). There is a reasonable causal relationship between study treatment and the AE. The event responds to withdrawal of study treatment (dechallenge) and recurs with rechallenge when clinically feasible.
- Probably Related – The AE is likely related to radiation and/or study drug(s). There is a reasonable causal relationship between study treatment and the AE. The event responds to dechallenge.
- Possibly Related – The AE may be related to radiation and/or study drug(s). There is a reasonable possibility that study treatment caused the adverse event. The investigator can provide a rationale or evidence to suggest a causal relationship between study treatment and the AE other than just a temporal relationship.
- Unlikely Related – The AE is doubtfully related to radiation and/or study drug(s). There is only a temporal relationship to study treatment, but not a reasonable causal relationship between study treatment and the AE.
- Unrelated – The AE is clearly NOT related to radiation and/or study drug(s). There is no temporal relationship to study treatment. There is a reasonable causal relationship to another drug product, concurrent disease, or circumstance.

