2.0 OBJECTIVES

Primary objective: Delivery of SBRT to multiple sites in a safe and effective manner with acceptable toxicity

Primary Endpoints:

- Presence of multiple sites (between 2 and 5 sites)
- Acceptable toxicity: Grade 3 or less

Secondary Objectives/Endpoints:

- Quality of life (as measured by the FACT quality of life surveys, see appendix IV)
- Local control of metastatic sites (with measurable/quantitative assessment): proportion of patients with Complete Response (CR), Partial Response (PR), or Stable Disease (SD)
- Local control of primary site (with measurable/quantitative assessment): proportion of patients with local Complete Response (CR), Partial Response (PR), or Stable Disease (SD)
- Overall survival (OS)
- Two-year Overall Survival
- Analysis of patterns of failure post-SRS/SBRT (subsequent sites of failure and time to failure): proportion of patients with Progressive Disease (PD)

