5.0 TREATMENT OVERVIEW

- Treatment of metastatic disease: all sites of metastatic disease will be treated with SRS or SBRT (see section 6.0)
- Treatment of primary disease: primary disease will be treated using surgery, chemotherapy, radiation, or a combination of all three (see section 6.0, 7.0, 8.0). Treatment of the primary disease will be as per the UPMC pathway guidelines or NCCN guidelines individualized for the patient's stage and disease site with the exception that the patient will be considered M0 instead of M1. (For example, T3N3M1 NSCLC would be considered T3N3M0 and treated with definitive chemoradiotherapy).
- Sequence of therapy: SRS/SBRT will be used for all sites of metastatic disease in close approximation to initiation of treatment for the primary disease site (within 6 weeks). Ideally, SRS/SBRT would occur first followed by treatment to primary site. However, in some circumstances surgical resection of the primary site could precede SRS/SBRT, especially if surgical resection is required for pathological confirmation of disease. After completion of SRS/SBRT to the oligometastatic sites and treatment to the primary site, systemic chemotherapy can be given at the discretion of the medical oncologists (see Section 7.0).

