10.3 Evaluation after study

10.3.1 Patients will be seen in follow-up with study physicians 6 weeks after completion of SRS/SBRT and then at 3 month intervals for 3 years and 6 months thereafter.

10.3.2 QOL survey to be performed prior to therapy, after SRS/SBRT and at subsequent follow-up visits using the FACT-G survey. See Appendix IV.

10.3.3 Toxicity will be evaluated after the study using Common Cancer Toxicity Criteria V 4.0

10.3.4 Follow-up imaging should be performed at least every 3 months for the first two years from completion of therapy and every 6 months afterwards until five years from the completion of therapy. FDG-PET/CT scan for follow-up is recommended but not required.

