11.0 STATISTICAL CONSIDERATIONS

Primary objective: Delivery of SBRT to multiple sites in a safe and effective manner with acceptable toxicity

Primary Endpoint(s):

- Presence of multiple sites (between 2 and 5 sites)
- Acceptable toxicity: Grade 3 or less

Secondary objectives/Endpoints:

- Quality of life (as measured by the FACT quality of life surveys, see appendix IV)
- Local control of metastatic sites
- Local control of primary site
- Overall survival (OS), Two-year Overall Survival
- Analysis of patterns of failure post-SRS/SBRT (subsequent sites of failure and time to failure)

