11.1 Objectives of the proposed study

The primary objective of the proposed phase II study is to evaluate the feasibility of this curative intent treatment approach (SRS/SBRT to the metastatic disease sites in combination with standard curative therapy to the primary site) to patients presenting with oligometastatic disease.

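### Section 12.3 asks for one causality rating across radiation and study drugs, so SBRT toxicity cannot be reliably separated from that of the other treatments

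*Combined protocol and SAP*

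**What the plan says.** The primary objective in the Summary, section 2.0 and section 11.0 is "Delivery of SBRT to multiple sites in a safe and effective manner with acceptable toxicity". The matching endpoint is "Acceptable toxicity: Grade 3 or less", with no statement of attribution, time window or acceptable rate. Section 11.1 gives the primary objective differently, as being to "evaluate the feasibility of this curative intent treatment approach", where the approach is SBRT together with standard curative therapy to the primary.

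On causality, section 12.3 says: "The investigator must determine the relationship between the administration of radiation and study drug(s) and the occurrence of an AE/SAE". Its five levels each rate the event against radiation, study drugs or both, taken together. Surgery is not named. The lowest level, for unrelated events, adds: "There is a reasonable causal relationship to another drug product, concurrent disease, or circumstance". Section 12.2.3 (Recording Requirements) asks for a causal assessment against study drugs only. The SAE form content listed under Reporting of Serious Adverse Events likewise asks only about relationship to study drug.

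On timing, section 5.0 places SBRT within 6 weeks of starting treatment of the primary, which may be surgery, chemotherapy, radiation or a combination. It prefers SBRT first but allows surgery to precede it. Section 10.3.1 says: "Patients will be seen in follow-up with study physicians 6 weeks after completion of SRS/SBRT".

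**The concern.** The exposure named in the primary objective is multi-site SBRT, but the causality record has no entry specific to it. A grade 4 event caused by SBRT to a metastasis and one caused by conventional radiotherapy to the primary are both rated simply as related to radiation. Chemotherapy events may share that rating, and surgical events have no clear place.

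The study is meant to prepare for a possible phase III trial (section 1.0). If the toxicity figure carried forward mixes SBRT with each patient's standard primary treatment, it may differ between cancer types because the primary treatment differs. An SBRT effect could also be lost among events expected from chemoradiotherapy.

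**Working it through.** **The plan's own figure.** Section 11.2 inflates 40 patients by 10%: 40 × 1.10 = 44, as stated. (Dividing instead gives 40 / 0.90 = 44.4, so 45; nothing here turns on that.) No acceptable or unacceptable toxicity rate, alpha or power is given, so there is no error rate to recompute. The illustration below uses the base of 40.

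**What each passage can separate**
- Section 12.3: one rating for radiation and drugs together, with no SBRT entry and no surgery entry. Several levels also use the term study treatment, which is not defined.
- Section 12.2.3 (Recording Requirements) and the SAE form list: relationship to study drug only, although the intervention under test is radiation.
- The two highest levels in section 12.3 require a response to withdrawal of treatment. Completed SBRT cannot be withdrawn, so a late SBRT effect can hardly be rated above possibly related.
- Against this, all adverse events are recorded whatever the suspected cause (section 12.2.3, Recording Requirements) and toxicities are graded (sections 10.2.2, 10.3.3 and 12.1).

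**What timing can separate**
- SBRT is completed within 3 weeks (section 6.2.1). External beam, chemotherapy and surgery are normally started after it (sections 6.1, 7.1 and 8.1). Acute events before primary treatment starts can therefore be assigned to SBRT in SBRT-first patients.
- A patient treated within the 6-week rule has, at the latest, reached the start of primary treatment by the first follow-up visit, 6 weeks after SBRT. Some will be further on.
- Appendix I has an adverse event evaluation during treatment, but nothing fixes one at the end of SBRT.
- Timing does not separate late effects, events after primary treatment begins, or events in surgery-first patients. Section 7.2 allows further chemotherapy after the primary is treated.

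**Possible size: an illustration on assumed rates**

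The documents give no grade 4 or higher rate for any modality. The nearest figures, in section 1.0, are 2% with grade 3 toxicity in a lung series and 2 of 29 = 6.9% with grade 3 or higher in a multi-site trial.

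Let p be the proportion with grade 4 or higher toxicity from SBRT, and q the rate from other therapy among the half of patients assumed to receive therapy carrying that risk. Assuming independence, the all-cause rate is 1 − (1 − p)(1 − 0.5q).
- p = 0.02, q = 0.20: 1 − 0.98 × 0.90 = 0.118, or 4.7 of 40. From SBRT: 0.02 × 40 = 0.8.
- p = 0.05, q = 0.30: 1 − 0.95 × 0.85 = 0.193, or 7.7 of 40. From SBRT: 0.05 × 40 = 2.0.

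For a wider range, let r be the rate from other therapy over all patients, so the all-cause rate is 1 − (1 − p)(1 − r).
- Lowest all-cause rate, p = 0.02, r = 0.05: 1 − 0.98 × 0.95 = 0.069, or 2.8 of 40.
- Highest all-cause rate, p = 0.07, r = 0.30: 1 − 0.93 × 0.70 = 0.349, or 14.0 of 40.
- Smallest SBRT share of affected patients, p = 0.02, r = 0.30: 0.02 / 0.314 = 6%.
- Largest SBRT share, p = 0.07, r = 0.05: 0.07 / 0.1165 = 60%.
- If r = 0, the all-cause and SBRT rates are equal.

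**The case against.** The strongest reply is that the endpoint as worded needs no attribution. All events are recorded and graded, so the proportion above grade 3 can be computed from any cause. Under section 11.1, where the objective is feasibility of the combined approach, that all-cause figure is a relevant one. Section 1.0 also calls the primary objective feasibility. This stands, and it rules out the inference that the primary question cannot be answered from the recorded data. It does not supply an SBRT-specific rate, which the objective in the Summary and sections 2.0 and 11.0 calls for.

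A second reply is that the usual SBRT-first order separates events by time. It does so in part, for acute events, so it would be wrong to say that timing gives no separation. The gaps are those listed in the working.

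A third is that pooling with chemotherapy is not certain. No study drug is defined, and chemotherapy is chosen at the oncologist's discretion. It might therefore fall under the other drug product named in the unrelated category, and surgery under the other circumstance. Section 7.0, headed Drug Therapy, points the other way, and the undefined term study treatment could take in surgery. The text is ambiguous. What is certain is that SBRT and conventional radiotherapy to the primary are not distinguished and that surgery is not named.

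**Conclusion.** The point holds in this form: an all-cause rate of toxicity above grade 3 can be computed, but the plan does not require SBRT-specific attribution, so SBRT toxicity cannot be reliably separated from that of the other modalities. The weakness is greatest for late effects, for events after primary treatment begins, and for surgery-first patients.

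The size is unknown. Under the first set of assumptions (SBRT 2–5%, half of patients on other therapy at 20–30%, independence) the all-cause rate is about 12–19%, or 5 to 8 of 40, against 1 to 2 of 40 from SBRT. The wider assumptions put SBRT's share of affected patients anywhere from about 6% to 60%.

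A reader might infer that the observed rate will mostly reflect primary treatment. The documents do not support that, because the rates are assumed and a 60% share for SBRT lies within the range. Nor do they show that SBRT would be judged unsafe because of chemotherapy, since section 11 sets no threshold for such a judgement. This is a worthwhile, inexpensive improvement to what is recorded, and it leaves the sample size of 44 unchanged.

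**What to change.** - **Attribution.** In section 12.3, in section 12.2.3 (Recording Requirements), and on both the AE and SAE forms, record relationship separately for (a) SRS/SBRT, (b) conventional radiotherapy to the primary, (c) systemic therapy and (d) surgery. When (a) is rated related, record which SBRT site is concerned.
- **Reporting.** In section 11, report the proportion of patients with an SRS/SBRT-related event above grade 3 beside the all-cause proportion. Count possibly, probably and definitely related as related, because the withdrawal criterion keeps late SBRT effects out of the upper levels. The pair serves both the SBRT objective in section 11.0 and the combined-approach objective in section 11.1.
- **Timing.** Place one of the existing during-treatment AE evaluations in Appendix I at the last SBRT fraction. This precedes primary treatment except in surgery-first patients, for whom it cannot serve as a clean cut.

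The cost is four ratings per event in place of one, a site field used only when SBRT is implicated, and a sentence in section 11. No visit is added, since the patient attends for the last fraction. The downside is that attribution by component is a matter of judgement, which is why the all-cause proportion is kept beside it.

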12.2.2 Abnormal Test Findings

An abnormal test finding will be classified as an adverse event if one or more of the following criteria are met:

- The test finding is accompanied by clinical symptoms.
- The test finding necessitates additional diagnostic evaluation(s) or medical/surgical intervention; including significant additional concomitant drug treatment or other therapy.

Note: simply repeating a test finding, in the absence of any of the other listed criteria, does not constitute an AE.

- The test finding leads to a change in study dosing or discontinuation of subject participation in the clinical study.
- The test finding is considered an AE by the Sponsor-Investigator of the IND application.

REPORTING OF SERIOUS ADVERSE EVENTS

All events meeting the definition of a serious adverse event, which occur after the date of first dose of study treatment and within **30** days of the last dose of study treatment, should be reported according to the departmental SAE checklist and SAE form. The initial SAE form should be sent to the following within 24 business hours / 1 business day of the Principal Investigator becoming aware:

1. Investigator: [contact]
2. [contact]
3. Local Institutional Review Board when reporting requirements are met.

In addition to completing appropriate patient demographic and suspect medication information, the report should include as applicable the following information that is available at the time of report within the Sections B and C of the departmental SAE form:

- CTCAE term(s) and grade(s)
- current status of study drug
- all interventions to address the AE (testing and result, treatment and response)

- hospitalization and/or discharge dates
- event relationship to study drug

Follow-up reports:

Additional information may be added to a previously submitted report by adding to the original departmental SAE form and submitting it as follow-up or creating supplemental summary information and submitting it as follow-up with the original departmental SAE form.

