6.2.2 Technical factors

SRS/SBRT has been formally defined and described in a published guideline from the American College of Radiology and American Society for Therapeutic Radiology and Oncology (47). This protocol will respect those guidelines. The term stereotactic for the purposes of this protocol implies the targeting, planning, and directing of therapy using beams of radiation along any trajectory in 3-D space toward a target of known 3-D coordinates. The coordinate system is defined by reliable “fiducial” markers. This differs from conventional radiation therapy, in which therapy is directed toward less-than-reliable skin marks or bony landmarks that are indirectly referenced to the tumor (surrogates). This protocol will require treatments to be conducted with the use of a fixed 3-D coordinate system defined by fiducials. The coordinate system defined by the fiducials should be directly related to the radiation-producing device (e.g., couch and gantry) in a reproducible and secure fashion. Capability should exist to define the position of targets within the patient according to this same 3-D coordinate system. As such, the patient is set up for each treatment with the intention of directing the radiation toward an isocenter or target according to the known 3-D coordinates as determined in the process of treatment planning. The nature of the fiducials themselves may include radiopaque markers or rods placed at known locations in a frame or fixed structure adjacent to the patient as well as use of the tumor itself as a fiducial (e.g., acquiring tomographic views of the tumor simultaneously with the treatment). Metallic “seeds” placed within the tumor will be allowed to constitute a fiducial so long as the methods are validated and a plan is in place to identify seed migration (e.g., redundant seeds placed). To allow fiducial stabilization and resolution of swelling, planning studies will be imaged 5-10 days after fiducial placement.

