APPENDIX I - Schedule of events

	Pre-Treatment	During Treatment	Follow-Up
Histo/cyto eval	X		
History/physical	X		X
Imaging of sites of disease (FDG-PET/CT)	X*		X
Performance status	X	X	X
CBC w/ diff & ANC	X		
Serum pregnancy test (if applicable)	X		
Informed consent	X		
Tumor response eval			X
Adverse event eval		X	X
QOL surveys	X		X

* If one was done within the past 8 weeks, then do not repeat.

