APPENDIX III - Guidelines for SRS/SBRT dosing and fractionation

Guidelines for SRS (see also section 6.2)

CNS

Treatment will be performed with single fraction SRS/SBRT. Patient will be positioned in supine position with appropriate fixation device, frameless SRS/SBRT can be performed if set-up uncertainty is minimal. SRS/SBRT doses are dependent on lesion size as follows:

Lesion Diameter (cm)	SRS/SBRT dose (Gy)
< 2	24/ 1 fx
2-3	18/ 1 fx
> 3	15 / 1 fx
> 4	30 / 3 fx

For larger lesions, fractionated SRS/SBRT may be used (3 fractions of 10 Gray per fraction) instead of a single fraction of 15 Gy.

LUNG

SBRT to lung lesions will consist of 3-5 treatments depending on location of tumor. Patient will be positioned in supine position with gated treatments or tumor tracking with fiducial markers. For central tumors (defined as within 2 cm of carina, right and left main bronchi, right and left upper lobe bronchi, intermedius bronchus, right middle lobe bronchus, lingular bronchus, and left lower lobe bronchus) SRS dose will be 48 Gy in 4 fractions. For non-central lesions, SBRT dose will be 60 Gy in 3 fractions.

Dose constraints for 48 Gy in 4 fractions:

Organ	Volume	Volume Max	Max Point Dose
Spinal Cord	<0.25 cc	22.5 Gy (4.5 Gy/fx)	30 Gy (6 Gy/fx)
Skin	<10 cc	30 Gy (6 Gy/fx)	32 Gy (6.4 Gy/fx)
Lung (both right and left lung volumes)	1500 cc	12.5 Gy (2.5 Gy/fx)	
Skin	< 10 cc	33.2 Gy (8.3 Gy/fx)	36 Gy (9 Gy/fx)
Chest wall	Any point	32 Gy (8 Gy/fx)	40 Gy (10 Gy/fx)

Dose constraints for 60 Gy in 3 fractions:

Organ	Volume	Max Point Dose
Spinal Cord	Any point	18 Gy (6 Gy per fx)
Esophagus	Any point	27 Gy (9 Gy per fx)
Heart/Pericardium	Any point	30 Gy (10 Gy per fx)
Bronchus	Any point	30 Gy (10 Gy per fx)
Skin	Any point	24 Gy (8 Gy per fx)
Chest wall	Any point	24 Gy (8 Gy per fx)

ADDRENAL

SBRT dose will be 50 Gy in 5 fractions. Patient will be positioned in supine position with gated treatments or tumor tracking with fiducial markers.

Dose constraints

Normal Tissue Constraints	
Organ	Maximum Dose in 5 Fractions
Contralateral Kidney (2/3 volume)	5 Gy
35% of Total (left & right) Kidney Volume	25 Gy
Spinal Cord	20 Gy
Stomach	35 Gy

BONE

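### SAE forms and scheduled AE evaluation begin with treatment and without a graded baseline, so whether harm from seed placement before the first dose counts as primary toxicity is undefined

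*Combined protocol and SAP*

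**What the plan says.** **SAE reporting.** The SAE paragraph sits under the section headed 12.2.2 Abnormal Test Findings. It requires a form for "All events meeting the definition of a serious adverse event, which occur after the date of first dose of study treatment", up to 30 days after the last dose.

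**Schedule.** In Appendix I the row "Adverse event eval" is marked for During Treatment and Follow-Up. The Pre-Treatment cell is empty.

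**Fiducials.** Section 6.2.2 requires a coordinate system defined by fiducials. It accepts external frame markers, the tumour itself, or metallic seeds placed in the tumour. On timing it says: "To allow fiducial stabilization and resolution of swelling, planning studies will be imaged 5-10 days after fiducial placement". For lung and adrenal lesions Appendix III says: "Patient will be positioned in supine position with gated treatments or tumor tracking with fiducial markers". For liver the choice is gating and/or fiducial tracking.

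**Causality.** Section 12.3 asks the investigator to relate an event to radiation and study drugs. It does not mention procedures needed to deliver the radiation.

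**Baseline.** Section 12.2.1 removes from the AE count "Medical conditions present at the initial trial visit that do not worsen in severity or frequency". Section 4.1 requires a history and physical before treatment, but no section asks for CTCAE grades at that point.

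**Primary endpoint.** Sections 2.0 and 11.0 call toxicity of grade 3 or lower acceptable. They give no time window, attribution rule, analysis set or threshold rate.

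**The concern.** The primary objective is safe delivery of SBRT to several sites. When seeds are implanted, placing them is an invasive step in that delivery, and for the first treated site it takes place before any radiation. The formal safety machinery (SAE form, scheduled AE evaluation, causality question) is worded around treatment that has already started, or around radiation and drugs alone.

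A serious placement complication could therefore be a real harm of the strategy under test and yet never reach the toxicity summary. In a trial of 44 patients, one grade 4-5 event changes the safety conclusion visibly.

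A lesser, related gap affects every patient. The rule on conditions that do not worsen needs a starting severity, and none is graded.

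**Working it through.** **1. Order of events for a first treated site with seeds.** Placement, then 5-10 days to planning imaging (Section 6.2.2), then planning, then the first fraction. The interval before the first dose is therefore at least 5 days plus planning time. For a later site, seeds could be placed after another site's first fraction and so fall inside the SAE window. The same complication would then be handled differently according to the order of sites.

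**2. What the first dose means.** The SAE paragraph does not define study treatment as SBRT. External beam radiation (6.1) and chemotherapy (7.1) follow radiosurgery. Surgery on the primary may come first (5.0) but has no dose. The first SBRT fraction is the natural reading, though not a stated one.

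**3. Which rules reach a serious placement complication before that dose?**

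| Rule | Stated start | Reaches it? |
|---|---|---|
| SAE form (12.2) | After first dose | No |
| Scheduled AE evaluation (Appendix I) | During treatment | No |
| Causality question (12.3) | None | Names only radiation and study drugs |
| IRB report (12.2.3) | None | Only if associated with study treatment; status of placement not stated |
| Questioning at study visits (12.2.2, Eliciting AE Information) | None | If a study visit falls in the interval |
| Case-history recording (12.2.3, Recording Requirements) | None | Yes, if observed or volunteered |
| Ongoing toxicity review (12.1) | During the study, start undefined | Possibly |

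The event would probably be written down. No rule ensures an SAE form, and none says that the event is counted.

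**4. Does the primary endpoint include it?** The endpoint has no window and no attribution rule, so the text neither includes nor excludes it.

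**5. Size.** The plan's own figure first: 40 x 1.10 = 44, as stated in Section 11.2. (Dividing instead, 40 / 0.90 = 44.4, which rounds up to 45.) The reporting window plays no part in this calculation.

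Only grade 4-5 events count against the endpoint. Exact two-sided 95% limits (Clopper-Pearson), supposing no other such event:

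- 0/44: upper limit = 1 - 0.025^(1/44) = 8.0%.
- 1/44 = 2.3%: upper limit = 97.5th percentile of Beta(2, 43) = 12.0%.
- With the 40 patients expected after drop-out: 0/40 has an upper limit of 8.8%; 1/40 = 2.5% has 13.2%.

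One missed event therefore moves the upper limit by about 4 percentage points.

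**6. How many might be missed?** The documents give neither the share of patients with seeds (s) nor the rate of grade 4-5 placement harm before the first dose (q). As assumptions only, take s from 25% to 100% and q from 1% to 5%. Expected events = 44 x s x q, and the chance of at least one = 1 - (1 - s x q)^44.

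- Low: 44 x 0.25 x 0.01 = 0.11 events; chance 10.4%.
- High: 44 x 1.00 x 0.05 = 2.2 events; chance 89.5%.

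The range is too wide to serve as a forecast. It shows only that a single missed event is plausible.

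**The case against.** The strongest reply is that the first-dose limit applies to the SAE form alone. Recording in case histories covers serious and non-serious events whatever the suspected cause, with no start date. Subjects are questioned at study visits, and Section 12.1 has all toxicities in the study evaluated under the NCI criteria. This stands. A reader might infer that AE evaluation as a whole begins only at the first SBRT dose, and the documents do not support that.

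A reader might also infer that placement harm falls outside the primary endpoint. That goes too far as well: nothing ties the endpoint to the SAE form or to the causality scale, so even an event rated unrelated is not removed by any stated rule. The position is undefined, with omission likely.

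Three further limits stand:

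- Seeds are allowed, not mandatory, and fiducial tracking is not named for CNS, bone or lymph node lesions.
- Serious does not mean grade 4-5. An admission makes an event serious whatever its grade, so counts of serious complications cannot be read as endpoint failures.
- The documents contain no figure showing that the reported toxicity would be too favourable specifically in multi-site patients.

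On baseline, the history and physical, performance status, CBC and FACT-G (which asks about pain, nausea and energy) are all collected before treatment. Baseline information therefore exists. What is missing is a CTCAE grade to compare with later grades, which makes this the lesser part of the point.

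None of this supplies an SAE form, a scheduled evaluation or a counting rule for a placement event before the first dose.

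**Conclusion.** The point holds as a gap in definition. A serious complication of seed placement before the first dose has no SAE form requirement and no scheduled AE evaluation, and the Section 12.3 question does not cover it. The primary endpoint does not say whether it counts.

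Each grade 4-5 event left out would change 0/44 to 1/44, taking the upper limit from 8.0% to 12.0%. How many would be left out cannot be derived from the documents. The conclusion rests on reading the first dose of study treatment as the first SBRT fraction, and it applies only to patients with implanted seeds. The absence of a graded baseline applies to everyone. The sample size is unaffected. This is an inexpensive improvement to safety capture and does not invalidate the design.

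**What to change.** - In Section 12.2, start AE and SAE collection at the first protocol procedure, including fiducial placement, or at consent if that is simpler. Align the SAE paragraph, the recording rule and Appendix I on that start.
- In Section 12.3, add protocol procedures, including fiducial placement, to the causality question.
- In Sections 2.0 and 11.0, give the toxicity endpoint a time window and state that these events count in the primary summary.
- In Appendix I, mark AE evaluation under Pre-Treatment, so that baseline CTCAE grades are recorded at the history and physical already scheduled.

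The cost is wording, with no new visit and no change to N. The downside is a few more SAE reports and possibly a slightly less favourable toxicity rate.
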